6.1.5. Serious ADE (SADE)

A SADE is defined as an adverse device effect that has resulted in any of the consequences characteristics of a serious adverse event

6.1.6. Unanticipated serious adverse device effect (USADE)

An USADE is defined as:

 Any serious adverse effect which by its nature, incidence, severity or outcome has not been identified in the current risk assessment

6.1.7. Anticipated serious adverse device effect (ASADE)

An ASADE is defined as:

 An effect which by its nature, incidence, severity, or outcome has been identified in the risk assessment.

6.1.8. Common treatment site responses (CTRs)

CTRs are common clinical presentations and/or side effects that a study subject may experience following treatment. Subjects will self-report CTRs, as defined a priori in the protocol, on diary cards provided to them. The treating investigator will review and initial the diary and determine if any entries should be reported as

AEs. A CTR that is more severe than what is generally expected and/or is not resolving should also be evaluated by the investigator as a possible AE, SAE, ADE, SADE, and/or UADE.

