2.1. Primary Objective

Evaluate the proportion of subjects with an improvement (score of 3 and above) at 6 months in the Global Aesthetic Improvement Scale (GAIS) with assessments of:

- MaiLi Volume as a treatment for mid-face volume deficit and temporal hollowing.
- MaiLi Extreme as a treatment for mid-face volume deficit, jawline ptosis and chin retrusion.

as determined by an on-site live independent evaluator.

Evaluate safety through the collection of all adverse events, inclusive of Serious Adverse Events (SAE), unanticipated problems, and Unanticipated Adverse Device Effects (UADE), experienced in the post-treatment follow-up period.

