Before the brand name MaiLi was chosen, the products were first identified as Hyalurogel B. Hyalurogel B2 corresponds to MaiLi Volume and Hyalurogel B3 corresponds to MaiLi Extreme (Clinical Evaluation Report, Hyalurogel B, 2020 18). Kylane Laboratories launched a clinical pilot study (reference 17E1176, version 1.0 of 27/06/2019) with 50 subjects (among which 30 subjects received MaiLi Volume or MaiLi Extreme). The purpose was to assess the efficacy and safety of all the products within the MaiLi range, including MaiLi Volume or MaiLi Extreme, and perform a comparison of MaiLi Extreme with the comparator Juvéderm VOLUMA (with lidocaine). The pilot study included two MaiLi products and additional treatment areas (e.g. lips and nasolabial folds) that are not part of the current proposed study. The pilot study was approved by the French Health Authority Agence nationale de sécurité du médicament et des produits de santé (ANSM) on 27th December 2017 (under ANSM registration number: A01694-49). The subjects were treated between 7th March 2018 until 9th March 2018 in the site of the Contract Research Organization (CRO) Dermscan (Lyon, France) by four different practitioners. This study was completed in 2019, after 12-month of clinical follow-up and it confirmed the safety and effectiveness of the MaiLi Volume/Extreme devices. Forty-five (45) adverse device effects were reported as related to one of the MaiLi devices. The frequency of the adverse device effects is shown in Table 1. All adverse device effects reported during the pilot clinical study were usual ones for injectable gels of hyaluronic acid and most of them lasted less than 10 days. No Serious Adverse Event (SAE) occurred during the study. Injectors were satisfied to very satisfied (depending on the item and device) of the performance of the MaiLi Volume/Extreme devices during injection. Independent evaluator and subjects reported that treated sites were globally improved aesthetically one month, six months and twelve months after treatment.

Table 1: Frequency Adverse Events

Frequent AE (≥10%)	Less frequent AE (<10%)	
 Hardness (induration)/firmness Lumps/bumps 	 Itching (pruritis) Discoloration (ecchymosis) Pain Tenderness Swelling (oedema) Bruising (haematoma) Redness (erythema) Itching (pruritis) Difficulty for eating Difficulty to drink Faint during injection Inflammatory reaction 	

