The content of the syringe is sterile until opening. The external surface of the syringe is not sterile and should not be used in a controlled environment such as an operation room. If needed, the surface of the syringe must be cleaned up in respect of the aseptic techniques in place.

Once the treatment is done, a safety assessment will be conducted and the investigator will do another photographic assessment of the subject. The investigator will complete the electronic case report form (eCRF) of the subject before giving instructions for the next follow-up appointment. The subject will be given a diary card to bring home and record any adverse reactions they experience. The subject will then bring back the diary card on their first follow-up appointment 2 weeks after the treatment. The diary card will be reviewed and documented down by the investigator.

For the subsequent follow-up visits (i.e. 3 months, 6 months, 12 months, 18 months, and 24 months after the treatment), the subject will be given a questionnaire to assess their overall satisfaction with the results of their treatment (see appendix 5).

During the study, two independent evaluators will be involved:

• An on site live independent evaluator (I) (one for each site (4)) will be responsible for

- conducting the live Global Aesthetic Improvement Scale (GAIS) assessment during the subject's scheduled visits at 3, 6, 12, 18, and 24 months (see appendix 7). This assessment will be done in comparison to the face of the subject (at the time of the visit) and the 'full face' photograph taken at the baseline visit.
- A blinded independent evaluator (II) (one per country (2)) will be responsible for the remote assessment of the photographs using the different aesthetic grading scales (namely: Allergan Mid-Face Volume Deficit Scale, Merz Aesthetics scale for Jawline, Allergan Chin Retrusion Scale, and/or Allergan Temple Hollowing Scale). This evaluator will do the assessment of the photographs of all performed visits at month 6 (to generate the data for the interim 6 months report) and 24 (for the final report) of the follow-up period.

Photographs will be taken at each visit, and assessed by a blinded independent evaluator at 6 months and 24 months.

All data collected for the study will be kept in a secure place and is only accessible to the study's team members.

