6.1.2. Adverse event (AE)

An AE is defined as any untoward medical occurrence, unintended disease or injury, or untoward clinical sign (including abnormal laboratory findings) in subjects, users or other persons, whether or not related to the investigational medical device and whether anticipated or unanticipated

- Note 1 to entry: This definition includes events related to the investigational medical device or the comparator.
- Note 2 to entry: This definition includes events related to the procedures involved.
- Notes 3 to entry: For users or other persons, this definition is restricted to events related to the use of investigational medical devices or comparators.

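### The primary safety objective covers all adverse events, yet 6.1.8 leaves it to each investigator, without a criterion or the promised list, which expected site responses count, so the AE rate may be under-counted and may differ between sites

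*Protocol*

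**What the plan says.** Protocol 2.1, repeated in 8.2, states the safety part of the primary objective: "Evaluate safety through the collection of all adverse events". Section 6.1.2 defines an AE broadly, "whether or not related to the investigational medical device and whether anticipated or unanticipated", and makes no exception for expected site reactions. Section 6.3.1 requires the investigator to record any AE or ADE in the subject's file and the eCRF, over a period that runs from signature of the consent form to the last visit.

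Section 6.1.8 then sets up a separate class: "Subjects will self-report CTRs, as defined a priori in the protocol, on diary cards provided to them". On what happens next it says "The treating investigator will review and initial the diary and determine if any entries should be reported as" AEs. One prompt follows: "A CTR that is more severe than what is generally expected and/or is not resolving should also be evaluated by the investigator". The categories named for that evaluation are AE and the more serious classes.

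On timing, the procedures text of section 5 (before 5.1) says "Once the treatment is done, a safety assessment will be conducted". In Table 8 the row for identifying and recording AEs is marked from week 2 onwards and is empty at baseline. Section 5.1.1 lists no post-injection safety assessment, and the synopsis lists six safety visits starting at week 2.

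**The concern.** Two rules govern the same events. Under 6.1.2 an expected swelling or lump that is an untoward sign is an AE. Under 6.1.8 it is a diary entry that may or may not become one, and the person who decides is the physician responsible for the treatment.

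The events left to discretion are likely to be the most frequent ones. Section 3 reports of the pilot study that "All adverse device effects reported during the pilot clinical study were usual ones for injectable gels of hyaluronic acid", and Table 1 puts induration and lumps in the group seen in 10% or more. If four sites draw the line differently, the primary safety result mixes device experience with reporting habit, and a comparison across sites, products or areas cannot separate the two.

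**Working it through.** The protocol states no AE rate for this trial, so there is no figure to reproduce. The check is mainly a comparison of texts, with an illustration of how far discretion could move a count.

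**1. Does the text give a criterion?** For an ordinary CTR, none: the investigator determines whether it is reported. For a CTR that is worse than generally expected or not resolving, 6.1.8 asks for evaluation, but sets no severity grade and no duration and does not define what is generally expected. The severity grades in 6.3.1.1 apply to events already classed as AEs.

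**2. Is there a CTR list?** Section 6.1.8 says the protocol defines CTRs in advance. No section or appendix carries such a list. Two lists could be mistaken for it. Neither is labelled as CTRs, and they differ:
- Table 1 (pilot AEs) includes fainting during injection, difficulty eating or drinking, and inflammatory reaction.
- The section 3 list of events that mostly resolve within a week includes bleeding, infection and granuloma, none of which is in Table 1.

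A site could use either, so the boundary of the class is open.

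**3. Direction.** Let N be the number of subjects, q the proportion with at least one CTR, and f the share of those subjects for whom the investigator reports an AE. Then

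- subjects with a CTR = N × q, the count under 6.1.2 if each CTR is an untoward sign;
- subjects reported under 6.1.8 = N × q × f.

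Since f cannot exceed 1, discretion can lower the count but not raise it. If f differs by site, the sites differ even when q is the same.

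**4. Illustration.** N = 168 in total and 42 per site come from the synopsis and 8.1. The values of q and f are assumptions, because the protocol gives neither. Other AEs in the same subjects are ignored.

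| Assumed q | CTR subjects, 168 × q | Reported at f = 50% | Reported at f = 25% | One site of 42: f = 10% to f = 90% |
|---|---|---|---|---|
| 30% | 50.4 | 25.2 (15%) | 12.6 (7.5%) | 1.3 to 11.3 |
| 50% | 84.0 | 42.0 (25%) | 21.0 (12.5%) | 2.1 to 18.9 |
| 80% | 134.4 | 67.2 (40%) | 33.6 (20%) | 3.4 to 30.2 |

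For example, one site with q = 50% gives 42 × 0.5 × 0.1 = 2.1 and 42 × 0.5 × 0.9 = 18.9. At f = 100% everywhere there is no loss.

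**5. Injection day.** Section 5 requires an assessment after treatment, 6.3.1 has AE observation already running on that day, and the diary issued under 5.1.1 starts on Day 1. Table 8, 5.1.1 and the synopsis visit list show no safety assessment on that day. The sources disagree on the schedule, but the day itself is covered.

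**The case against.** The best defence is that 6.1.8 does not exempt CTRs from 6.1.2. The investigator can apply the AE definition to each diary entry, 6.3.1 obliges recording of any AE or ADE, and the remark about severe or persistent responses only adds a prompt. Diaries are kept, reviewed and documented (section 5), data are monitored against source (10.1), and an analysis plan not at hand may tabulate CTRs separately.

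Part of this stands: no loss of events has been shown. But a separate class with its own decision step has a purpose only if some entries are not reported as AEs, and nothing tells sites which. A separate tabulation would also need CTR data that are entered completely, and 6.1.8 does not require each diary entry to reach the eCRF. An analysis plan cannot restore uniform classification after sites have judged differently.

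Three stronger inferences are tempting, and the protocol does not support them.
- *Safety recording starts at week 2, so injection-day events are lost.* Section 5 requires the assessment, 6.3.1 covers the day, the Day 1 diary captures it, and the week 2 visit records any adverse events.
- *The pilot gives the size, with its 45 device effects reportable as anything from none to all.* Those effects span the whole product range and areas outside this study, and only 30 of the 50 subjects received Volume or Extreme. None is not a plausible floor: fainting is not a site response, and only most effects lasted under 10 days.
- *The AE rate cannot be compared with the pilot's.* The protocol does not say how pilot observations became device effects, so this cannot be judged, and no such comparison is an objective here.

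**Conclusion.** The conflict between 2.1 and 6.1.2 on one side and 6.1.8 on the other is in the text, and the CTR list that 6.1.8 relies on is absent. The AE rate in the primary safety result may be under-counted relative to 6.1.2 and may differ between the four sites. This is a risk created by the recording rule, not a demonstrated bias.

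Its size cannot be derived from the protocol, and the table above only shows what assumed values would do. The conclusion rests on two assumptions: that ordinary site responses meet the AE definition as untoward signs, and that no diary form or site instruction outside the protocol already fixes the list and the rule. The point is worth correcting because it affects the most common events in a primary objective. The injection-day mismatch is a lesser, editorial matter.

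**What to change.** In 6.1.8:
- give the closed CTR list and use the same list on the diary;
- require every diary-recorded site response to be entered in the eCRF;
- apply one rule at all sites, either counting each response as an AE/ADE with a CTR flag, or reporting all CTRs beside the AEs in the primary safety results.

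Show total, CTR and non-CTR results per product, with subjects treated with that product as denominator, and per area, with subjects treated in that area as denominator. All treated subjects would be the wrong denominator for an area, because 4.1 allows treatment in one or several areas and each subject contributes only to those treated.

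Separately, reconcile Table 8, 5.1.1 and the synopsis visit list with the procedures text of section 5 and with 6.3.1 on the injection-day safety assessment.

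The cost is some extra data entry from diaries that are already collected, which under 5.1.2 run to month 24, and a higher headline AE rate if CTRs are counted as AEs. Patient care and the visit plan are not affected by the counting rule.

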6.1.9. Device deficiency

A device deficiency is defined as any inadequacy of a medical device with respect to its identity, quality, durability, reliability, usability, safety or performance.

- Note 1 to entry: Device deficiencies include malfunctions, use errors, and inadequacy in the information supplied by the manufacturer including labelling.
- Note 2 to entry: This definition includes device deficiencies related to the investigational medical device or the comparator.

6.1.10. Malfunction

Malfunction is defined as failure of an investigational medical device to perform in accordance with its intended purpose, when used in accordance with the instructions for use or CIP, or IB.

6.2. Reportable events

Only Serious Adverse Events (SAEs) where a causal relationship between the serious adverse event and the preceding investigational procedure has been established are considered reportable events.

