6.2.1. Causality assessment

The relationship between the use of the medical device (including the medical - surgical procedure) and the occurrence of each adverse event shall be assessed and categorized.

During causality assessment activity, clinical judgement shall be used and the relevant documents, such as the Investigator's Brochure, the Clinical Investigation Plan (CIP) or the Risk Analysis Report shall be consulted, as all the foreseeable serious adverse events and the potential

risks are listed and assessed there. The presence of confounding factors, such as concomitant medication/treatment, the natural history of the underlying disease, other concurrent illness or risk factors shall also be considered.

The above considerations apply also to the serious adverse events occurring in the comparison group.

For the purpose of harmonizing reports, each SAE will be classified according to four different levels of causality:

- 1. Not related
- 2. Possible
- 3. Probable
- 4. Causal relationship

The sponsor and the investigators will use the following definitions to assess the relationship of the serious adverse event to the investigational device, the comparator or the investigation procedure.

- 1. Not related: Relationship to the device, comparator or procedures can be excluded when:
 - the event has no temporal relationship with the use of the investigational device, or the procedures related to application of the investigational device;
 - the serious adverse event does not follow a known response pattern to the medical device (if the response pattern is previously known) and is biologically implausible;
 - the discontinuation of medical device application or the reduction of the level of activation/exposure - when clinically feasible - and reintroduction of its use (or increase of the level of activation/exposure), do not impact on the serious adverse event:
 - the event involves a body-site or an organ that cannot be affected by the device or procedure;
 - the serious adverse event can be attributed to another cause (e.g. an underlying or concurrent illness/ clinical condition, an effect of another device, drug, treatment or other risk factors);
 - the event does not depend on a false result given by the investigational device used for diagnosis9, when applicable; In order to establish the non-relatedness, not all the criteria listed above might be met at the same time, depending on the type of device/procedures and the serious adverse event.

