- 2. Possible: The relationship with the use of the investigational device or comparator, or the relationship with procedures, is weak but cannot be ruled out completely. Alternative causes are also possible (e.g. an underlying or concurrent illness/ clinical condition or/and an effect of another device, drug or treatment). Cases where relatedness cannot be assessed, or no information has been obtained should also be classified as possible.

- 3. Probable: The relationship with the use of the investigational device or comparator, or the relationship with procedures, seems relevant and/or the event cannot be reasonably explained by another cause.
- 4. Causal relationship: The serious adverse event is associated with the investigational device, comparator or with procedures beyond reasonable doubt when:
 - the event is a known side effect of the product category the device belongs to or of similar devices and procedures;
 - the event has a temporal relationship with investigational device use/application or procedures;
 - the event involves a body-site or organ that
 - the investigational device or procedures are applied to;
 - o the investigational device or procedures have an effect on;
 - the serious adverse event follows a known response pattern to the medical device (if the response pattern is previously known);
 - the discontinuation of medical device application (or reduction of the level of activation/exposure) and reintroduction of its use (or increase of the level of activation/exposure), impact on the serious adverse event (when clinically feasible);
 - other possible causes (e.g. an underlying or concurrent illness/ clinical condition or/and an effect of another device, drug or treatment) have been adequately ruled out;
 - harm to the subject is due to error in use;
 - the event depends on a false result given by the investigational device used for diagnosis, when applicable;

In order to establish the relatedness, not all the criteria listed above might be met at the same time, depending on the type of device/procedures and the serious adverse event.

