The sponsor and the investigators will distinguish between the serious adverse events related to the investigational device and those related to the procedures (any procedure specific to the clinical investigation). An adverse event can be related both to procedures and the investigational device. Complications caused by concomitant treatments not imposed by the clinical investigation plan are considered not related. Similarly, several routine diagnostic or patient management procedures are applied to patients regardless of the clinical investigation plan. If routine procedures are not imposed by the clinical investigation plan, complications caused by them are also considered not related.

In some particular cases the event may not be adequately assessed because information is insufficient or contradictory and/or the data cannot be verified or supplemented. The sponsor and the Investigators will make the maximum effort to define and categorize the event and avoid these situations. Where an investigator assessment is not available and/or the sponsor remains uncertain about classifying the serious adverse event, the sponsor should not exclude the relatedness; the event should be classified as "possible" and the reporting not be delayed.

Particular attention shall be given to the causality evaluation of unanticipated serious adverse events. The occurrence of unanticipated events related could suggest that the clinical investigation places subjects at increased risk of harm than was to be expected beforehand.

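### Section 6.2 limits SAE reporting to authorities to established causal relationships, while Section 6.2.1 wants uncertain SAEs classed as possible and reported without delay

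*Protocol*

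**What the plan says.** Section 6.2 gives the rule for what is reportable: "Only Serious Adverse Events (SAEs) where a causal relationship between the serious adverse event and the preceding investigational procedure has been established". The only cause it names is the investigational procedure.

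Section 6.2.1 states that "each SAE will be classified according to four different levels of causality": not related, possible, probable and causal relationship. Three of the definitions matter here.

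- *Possible* is a weak relationship that cannot be ruled out. It also takes in events without enough information: "Cases where relatedness cannot be assessed, or no information has been obtained should also be classified as possible".
- *Probable* applies where the relationship "seems relevant and/or the event cannot be reasonably explained by another cause".
- *Causal relationship* opens with "The serious adverse event is associated with the investigational device, comparator or with procedures beyond reasonable doubt when", followed by a list of criteria.

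Section 6.2.1 also has an instruction for doubtful cases. Where there is no investigator assessment, or the sponsor remains uncertain, "the sponsor should not exclude the relatedness"; the event is to be classed as possible "and the reporting not be delayed".

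Section 6.2.2 sets the sponsor's limits for reporting to competent authorities: 2 calendar days for events that indicate an imminent serious risk, 7 calendar days for any other. Section 6.2.3 names the national competent authorities as recipients. Both sections apply to reportable events only. Section 6.3.2 separately requires the investigator to send all SAEs and SADEs, related or not, to the sponsor and the CRO within 72 hours.

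**The concern.** The definition in Section 6.2 decides which events enter the 2-day and 7-day limits. Followed to the letter, it keeps an SAE of uncertain cause out of expedited reporting to authorities, although Section 6.2.1 says that reporting of such an event must not wait. A person in the sponsor's vigilance function who holds an SAE classed as possible can therefore cite the protocol for either course.

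The events at issue could be grave. Section 3 lists rare ischaemic events of the eye and brain among the undesirable effects of injectable fillers. A serious event with a plausible alternative explanation fits the definition of possible, which is where the two sections disagree.

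**Working it through.** No sample size, error rate or count enters this point, so there is nothing to calculate. The check sets the sections side by side.

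**Step 1. What does established mean in Section 6.2?** Section 6.2 does not refer to the four-level scale. It does use the term causal relationship, which in Section 6.2.1 is the name of level 4. Within Section 6.2.1, establishing relatedness is spoken of only under that level: "In order to establish the relatedness, not all the criteria listed above might be met at the same time". In the protocol's own vocabulary, level 4 is thus the only level that clearly meets Section 6.2.

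**Step 2. What does Section 6.2.1 require?** Its instruction on doubtful cases addresses the sponsor and applies even when no investigator assessment exists. It stands under the Section 6.2 heading on reportable events, just before the sponsor's time limits for authorities. The reporting that must not be delayed is therefore most naturally the sponsor's reporting to authorities.

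**Step 3. Compare level by level.**

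| Level in 6.2.1 | Reportable under 6.2 as worded? | What 6.2.1 says on reporting |
|---|---|---|
| Not related | No | Nothing |
| Possible | Not on the reading in step 1 | Do not delay, for events classed here because of uncertainty or a missing assessment |
| Probable | Not on the reading in step 1 | Nothing |
| Causal relationship | Yes | Nothing further |

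The row for possible contains a direct conflict. The row for probable is unsettled: Section 6.2 as worded leaves it out, although it is a stronger relationship than one whose reporting must not be delayed.

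**Step 4. Device and procedure.** Section 6.2 names the procedure alone. Section 6.2.1 asks the sponsor and investigators to separate SAEs related to the device from those related to procedures, and allows an event to be related to both. Section 6.2 does not say whether a relationship to the device alone is enough.

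**Step 5. Does another section settle it?** Section 6.3.2 ensures that the sponsor receives every SAE. Its onward step, to regulatory agencies, ethics committees and investigators, is conditional on being applicable, and it does not say when that is so. That leads back to Section 6.2.

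**The case against.** The strongest reply is that the practical risk is small. Every SAE reaches the sponsor and the CRO within 72 hours without a causality filter (Section 6.3.2), and every adverse event is recorded in the eCRF (Section 6.3.1). For uncertain SAEs, the specific instruction in Section 6.2.1 may be taken to prevail over the general rule in Section 6.2. The first part stands and limits the point to onward reporting. The second is a reasonable working habit, but Section 6.2 begins with the word only and makes no exception.

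It can also be said that Section 6.2 never mentions level 4 and that established might loosely mean not excluded. It is true that the link to level 4 is read from shared wording and is not stated. Nothing in the text supports the looser sense, however.

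On device and procedure, Section 6.2.1 opens by including the procedure within use of the device, and the procedure here is the injection of the device. Reading Section 6.2 as excluding device effects would be strained. What remains is a need for clarification, as Section 6.2.1 later separates the two.

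A reader might infer more than the protocol supports:

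- **That SAEs go unreported in general, or that the primary safety objective is compromised.** That objective rests on collecting all adverse events. Section 6.2 restricts neither collection nor recording nor classification.
- **That sites would handle the same SAE differently.** Sites do not apply Section 6.2; they send every SAE. Inconsistent handling could arise only on the sponsor's side.
- **That Section 6.2.1 makes three of the four levels reportable.** It does not say so. Its instruction covers uncertain events classed as possible and does not mention probable ones.

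**Conclusion.** The conflict is real and narrow. Sections 6.2 and 6.2.1 give incompatible directions for at least those SAEs classed as possible because of uncertainty or a missing assessment. They leave probable SAEs without a settled status. The effect is confined to the sponsor's reporting to competent authorities under Sections 6.2.2 and 6.2.3. No endpoint, sample size or safety estimate changes.

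The number of SAEs affected cannot be derived from the protocol. The conclusion rests on two readings: that causal relationship in Section 6.2 has the meaning it is given in Section 6.2.1, and that the reporting not to be delayed is the sponsor's reporting to authorities. Both are the natural readings, but the protocol states neither outright. An amendment is justified because the definition controls all expedited reporting to authorities and is easy to repair.

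**What to change.** Amend Section 6.2 to name which of the four causality levels are reportable, in terms consistent with the Section 6.2.1 instruction on uncertain SAEs. The status of probable SAEs should be stated explicitly. The same sentence should say that a relationship to the device counts as well as one to the procedure, as in Section 6.2.1. The sponsor's vigilance function should confirm the wording, because which levels must go to authorities depends on reporting requirements that the protocol does not reproduce.

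The cost is a one-sentence amendment and possibly a few more expedited reports. Data collection and site procedures do not change.
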